Based primarily on results from studies in healthy volunteers, standard dose reductions of RBT have been recommended when administered with PIs, but there is a critical need to validate those recommendations among participants with HIV-related TB. Notably, the reduced dose of RBT would likely be inadequate for TB treatment if the PI therapy was discontinued. Therefore, the approach of reduced dose RBT relies on adherence to a PI and there may be differences among PIs with regard to the impact on PK/PD. In one small study, 10 HIV-infected participants hospitalized in a TB treatment facility were started on RBT-based TB treatment at a dose of 300 mg TIW without LPV/r, had week 2 RBT concentrations obtained, then added a LPV/r-based ART regimen and reduced their RBT dose to 150 mg TIW, per current recommendations. The  $C_{max}$  obtained at week 4 to 5 was  $\leq 0.30 \mu\text{g}/\text{mL}$  for 9 of 10 participants while the partially active 25-O-desacetyl metabolite of RBT was increased, as was the  $AUC_{0-24}$  and  $AUC_{0-48}$ . Most unbound RBT  $C_{max}$  values were below the minimum inhibitory concentration (MIC) for drug-susceptible MTB and values for the plasma concentration-time curve were below those that had been associated with TB treatment failure or relapse (i.e., an  $AUC_{0-24} < 4.5 \mu\text{g}^*\text{h}/\text{mL}$ ) in a previously conducted TB Trials Consortium Study. Eight of the 10 participants in the study were men with a median weight of 74 kg and a median body mass index (BMI) of 23.1, a heavier population with a different gender proportion than participants likely to be enrolled from some resource-constrained settings. In another report, three participants experienced a relapse of TB with a RIF-resistant isolate after treatment with a RTV-boosted PI-based ART regimen coupled with a RBT-based TB regimen using a 150 mg TIW dose schedule. These studies raise some uncertainty about current dosing recommendations for RBT in the setting of PI-based therapy, although results from a recent PK study conducted in South Africa shed further light on this issue. In this study, the PK of RBT was evaluated in 16 HIV coinfected participants with active TB. These participants were initially treated with a RBT-based anti-TB regimen (using RBT in a dose of 300 mg daily) before starting ART that included standard doses of LPV/r 400/100 mg BID daily. Participants were established on their anti-TB therapy and were then randomized after starting LPV/r to receive RBT 150 mg daily x 4 weeks followed by 150 mg TIW or to the converse dosing strategy. Serial RBT and 25-O-desacetyl RBT concentrations were measured after each 4 week interval. The median  $AUC_{0-24}$ , and  $C_{max}$  on RBT 300 mg daily, 150 mg TIW, and 150 mg daily, respectively, were 3026 ng/mL.h and 297 ng/mL, 2307 ng/mL.h and 168 ng/mL, and 5010 ng/mL.h and 311 ng/mL. All doses were well tolerated with only one case of uveitis that occurred prior to starting LPV/r and one episode each of Grade 2 transaminitis and neutropenia reported. When coupled with standard doses of LPV/r, the dose of RBT that best approximated the 300 mg dose in the absence of LPV/r, and that achieved a  $C_{max}$  concentration of RBT within recommended target ranges for TB treatment of 300-900 ng/mL, was the RBT 150 mg daily dose. These data in aggregate suggest that in the context of PI-based therapy, the current recommended dose of RBT is insufficient. Finally, RBT is not available in fixed-dose combination formulations of TB medications that are commonly used in high-burden settings. Therefore, the use of RBT, rather than RIF, will be associated with higher pill burdens and will be more complex for patients and TB control programs.

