C	LPV 400 mg/RTV 100 mg tabs BID + two NRTIs + RAL 400 mg BID	INH 300 mg daily, RBT 300 mg daily, then 150 mg daily upon initiation of ART*, EMB (weight-based dose) daily, PZA (weight-based dose) daily, and pyridoxine 25 mg daily. EMB and PZA will be discontinued after 8 weeks of treatment; INH, RBT 150 mg daily (or the adjusted dose determined by PK), and pyridoxine will continue for a minimum total duration of 24 weeks. INH, RBT, and pyridoxine may continue beyond the 24 weeks to a maximum of 48 weeks at the discretion of the primary clinician; the protocol core team must be notified.	LPV/r + two NRTIs + RAL will continue at standard dosing through week 72	This regimen follows the same rationale as for Arm A but adds RAL in an attempt to enhance the antiviral activity of LPV/r when combined with RBT to evaluate whether this approach is associated with a better virologic response than the other two arms.

\*NOTE: In Arms A and C, RBT should be administered at a dose of 300 mg daily until the start of antiretroviral therapy at which time the dose should be reduced to the 150 mg daily dose. If LPV/r is stopped prematurely during TB treatment, the RBT dose should be increased to 300 mg daily and the team should be notified. All participants will receive TB treatment according to in-country TB guidelines for daily TB treatment and directly observed therapy (DOT), except that all study participants will receive daily TB treatment 7 days per week, i.e., participants will not use a 5 days per week schedule that may be recommended in some in-country TB programs.

Accrual will take place in two accrual periods. Accrual period 1 will enroll participants who will undergo an initial dose-finding period before continuing regular study follow-up through 72 weeks. Once review of the dose-finding data in accrual period 1 is completed, accrual period 2 will begin.

#### Accrual Period 1

Sixty participants will be randomized 1:1:1 (20 participants per arm) to one of three treatment arms as detailed above. Anti-TB therapy with study-provided RBT or non-study-provided RIF and non-study-provided INH, EMB, and PZA should be started within 72 hours of randomization. ART should be started as soon as possible after initiating anti-TB therapy, but may be delayed for up to 7-14 days after starting anti-TB therapy to allow participants sufficient time to assess tolerability of TB medications. Participants will then undergo a formal PK and safety evaluation to include:

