If, based on the SMC's determination, unacceptable PK or safety criteria are met within two treatment arms, then further enrollment into the study may be stopped, and the accrual period 1 participants will be managed according to best available local TB and antiretroviral treatment. These participants will be followed off study medication for the remainder of study follow-up (up to 72 weeks).

Table 5.1. LPV/r and RBT Dose Adjustment Table

	LPV/r Dose Adjustment	Rifabutin Dose Adjustment
Arm A	No dose adjustment	
RBT PK parameters low: Adjust RBT to RBT 300 mg orally three times weekly (TIW) or 300 mg orally once daily (see section 10.4).
 
RBT PK parameters high: Decrease RBT to RBT 150 mg orally TIW
 
NOTE: The RBT <math>C_{max}</math> will be used for the purpose of individual dose adjustment for low or high RBT concentrations. A low RBT concentration will be < 250 ng/mL. A high

		RBT $C_{max}$ will be greater than 900 ng/mL.
Arm B	
 
LPV <math>C_{min}</math> < 1 mg/L and <math>C_{max}</math> < 12 mg/L: add LPV 200 mg/RTV 50 mg (one additional fixed-dose combination tablet) twice daily
 
LPV <math>C_{min}</math> < 1 mg/L and <math>C_{max}</math> > 12 mg/L: add one additional RTV 100 mg tab tablet twice daily
 
 
NOTE: A LPV <math>C_{12}</math> (or trough) will be used to define whether an individual subject's LPV/r dose is too low.
	N/A
Arm C	No dose adjustment	
RBT PK parameters low: Adjust RBT to RBT 300 mg orally TIW or 300 mg orally once daily (see section 10.4).
 
RBT PK parameters high: Decrease RBT to RBT 150 mg orally TIW
 
NOTE: See Arm A for definition of RBT low and high concentrations.

Rifabutin Dose Adjustment:

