RBT concentrations clearly associated with therapeutic success or an increased incidence of toxicity have not been established, although the range of 300-900 ng/mL for  $C_{max}$  has been associated with acceptable TB outcomes in a small number of patients. The RBT  $C_{max}$  will be used for the purpose of individual dose adjustment for low or high RBT concentrations. A low RBT  $C_{max}$  will be defined as < 250 ng/mL. This concentration represents the 25th percentile of RBT  $C_{max}$  values in 14 HIV and TB infected persons receiving a RBT dose of 150 mg once daily given in conjunction with LPV/RTV. A high RBT  $C_{max}$  will be greater than 900 ng/mL. This concentration is greater than 2 standard deviations in healthy volunteers receiving a 300 mg once daily RBT dose. The 300 mg RBT once daily dose is the usual RBT dose prior to an adjustment for the drug-drug interaction with LPV/RTV; a  $C_{max}$  > 900 ng/mL would represent an exposure above that usually seen in healthy volunteers or persons with TB.

LPV/r Dose Adjustment:

A LPV  $C_{12}$  (or trough) less than 1 mg/L will be used to define whether an individual participant's LPV/r dose is too low. A  $C_{12}$  value less than 1 mg/L is less than the 25th percentile of  $C_{12h}$  concentrations in a small study of HIV and TB infected persons receiving double dose LPV/RTV (i.e. 800/200 twice daily) with RIF, 600 mg once daily. A 12-hour post dose plasma concentration ( $C_{12h}$ ) value less than 1 mg/L is also considered the minimum threshold value for LPV by the DHHS Guidelines Panel. A  $C_{max}$  value > 12 mg/L is  $\geq$  the 75th percentile in HIV-infected persons receiving the usual twice daily 400/100 LPV/RTV dose.

NOTE: No substantive effect of RBT on LPV concentrations is expected based on prior PK data with this combination; however, if LPV levels in the ranges noted for Arm B are observed in Arm A or Arm C, then dose adjustments will be the same as for Arm B.

#### 5.1.2 For Participants Enrolled During Accrual Period 2

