#### 7.2.4 Neutropenia

Participants entering this trial will potentially have advanced HIV disease and active TB. Neutropenia is expected. Because this study is designed to assess the risk/benefit ratio of second-line ART with varying doses of LPV/r and RBT as an alternative for RIF in this population, participants with  $\geq$  Grade 2 neutropenia will be allowed to enroll in accrual period 1 and participants with  $\geq$  Grade 3 neutropenia will be allowed to enroll in accrual period 2 of the study. RBT may be associated with neutropenia. If Grade 4 neutropenia develops after study entry and RBT is considered the likely causative agent, the dose of RBT should be reduced according to recommendations in Table 5.1, and the neutrophil count should be repeated within 72 hours of the dose reduction. If the participant is already receiving a reduced dose of RBT, or if the repeat neutrophil count has not improved to Grade 3 or less, then RBT should be held, and the neutrophil count should be repeated within 72 hours. If the neutrophil count has improved to Grade 3 or less, RBT may be restarted at the reduced dose. If Grade 4 neutropenia recurs, RBT must be permanently discontinued, the participant should be referred to his/her primary clinician or local TB program, and provided the best available anti-TB therapy according to local standards, and the participant should continue to be followed on study but off study-provided anti-TB medications.

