### 9.2.3.3 Safety and tolerability:

9.2.3.3.1 Highest reported grade of each new Grade 3 or 4 laboratory value or sign or symptom that is at least a one grade increase from baseline.

9.2.3.3.2 Ordered categorical variable indicating most stringent level of ARV drug management due to toxicity that was required over the co-treatment period: premature permanent treatment discontinuation; treatment hold for more than 3 consecutive days; and none of the above.

9.2.3.3.3 Ordered categorical variable indicating most stringent level of TB drug management due to toxicity that was required over the co-treatment period: premature permanent treatment discontinuation; treatment hold for more than 7 consecutive days; and none of the above.

9.2.3.4 HIV virologic failure is defined as two consecutive plasma HIV-1 RNA levels  $\geq$  1000 copies/mL at or after 16 weeks and before 24 weeks of ART or  $\geq$  400 copies/mL at or after 24 weeks of treatment.

NOTE: This definition of virologic failure will be applied regardless of whether or not randomized ART is being taken at the time of failure.

9.2.3.4.1 Occurrence of HIV virologic failure.

9.2.3.4.2 Time to HIV virologic failure.

9.2.3.5 TB drug resistance patterns in participants who have TB treatment failure or relapse/recurrence of TB.

9.2.3.6 Occurrence of MTB IRIS events.

9.2.3.7 Predictors of disease progression:

9.2.3.7.1 CD4+ T-cell counts at baseline and at weeks 8, 24, 48, and 72.

9.2.3.7.2 Occurrence of new AIDS-defining illnesses.

9.2.3.7.3 Occurrence of HIV-disease progression (defined as new AIDS-defining illness or death).

9.2.3.7.4 Occurrence of death.

9.2.4 Additional endpoints for supportive/exploratory analyses that will be defined in more detail in separate analysis plans:

9.2.4.1 HIV-1 drug resistance patterns in participants who have HIV virologic failure.

9.2.4.2 LPV plasma concentrations in Arm B, RBT plasma concentrations in Arms A and C, and RAL plasma concentration in Arm C at weeks 2 and 8 in accrual period 2 participants.

9.2.4.3 Cost-benefit measures related to adding RAL.

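### The TB-drug tolerability endpoint (9.2.3.3.3) cannot show a toxicity dose reduction of rifabutin, a step the protocol itself directs in Arms A and C

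*Protocol*

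**What the plan says.** Protocol 9.2.3.3.3 defines an ordered variable for the strictest TB-drug management needed because of toxicity during co-treatment. The top level is premature permanent discontinuation; the rest read "treatment hold for more than 7 consecutive days; and none of the above". Dose reduction has no level.

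Protocol 7.2.4 sets out what to do when Grade 4 neutropenia develops and RBT is the likely cause:

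- First, "the dose of RBT should be reduced according to recommendations in Table 5.1", with a repeat count within 72 hours. The only decrease in Table 5.1, for Arms A and C, is "Decrease RBT to RBT 150 mg orally TIW".
- If the participant is already on a reduced dose, or the count has not improved to Grade 3 or less, "then RBT should be held, and the neutrophil count should be repeated within 72 hours". On improvement, RBT may restart at the reduced dose.
- If Grade 4 neutropenia recurs, RBT is stopped for good.

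Section 7.0 leaves toxicity management of the other TB drugs, including rifampin in Arm B, to local programmes or the site investigator. The SAP does not define this endpoint. Its tolerability tables (section 4.2) count discontinuations only.

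**The concern.** Objective 1.3.4 compares safety and tolerability between the arms, and 9.2.3.3.3 is the only TB-drug management measure listed for it. A variable described as the most stringent management required should be able to show a step that the protocol itself directs for a Grade 4 toxicity. As defined, it cannot. Someone moved to 150 mg three times weekly for Grade 4 neutropenia is indistinguishable from someone whose TB drugs were left alone.

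RBT is the only TB drug with a reduction rule in the protocol, so the unseen step probably falls mainly on Arms A and C. The pathway is foreseeable: Protocol 2.1 names neutropenia as a toxicity of the raised RBT concentrations that protease inhibitors cause. What is at stake is the completeness of a secondary tolerability comparison. The primary virologic analysis is not touched.

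**Working it through.** The plan states no rate, power or sample size for this endpoint, so there is no figure to reproduce. The check traces the management rules through the endpoint levels and then sizes the gap.

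**1. Neutropenia pathway (7.2.4) against the levels of 9.2.3.3.3**

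| Course | Hold | Level |
|---|---|---|
| Dose reduced, count improved at the recheck within 72 h | none | none of the above |
| Dose reduced, no improvement, RBT held, improved at the second recheck within 72 h, restarted | about 3 days | none of the above |
| Hold goes on beyond 7 days | > 7 days | hold |
| Grade 4 recurs | permanent stop | discontinuation |

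The first two courses take at most about 3 + 3 = 6 days, with a hold of at most about 3 days, so neither reaches the 7-day threshold. The general Grade 4 rule in 7.1, which withholds all drugs, covers only symptomatic events not specifically addressed later. Neutropenia is addressed in 7.2.4.

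**2. Other RBT toxicities**

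- AST/ALT and bilirubin (7.2.1, 7.2.2): the TB drugs return one at a time at 3-7 day steps, with RBT last. In the four-drug phase three drugs precede it, so RBT returns 3 × 3 = 9 to 3 × 7 = 21 days after rechallenge starts. These holds are already ranked.
- Uveitis (7.2.3): RBT is held until symptoms resolve, then may restart at a reduced dose. The length of the hold is not stated, so a case with a hold of 7 days or less would be unranked.

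**3. Size of the unranked step**

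- Weekly dose: 150 × 7 = 1,050 mg daily dosing; 150 × 3 = 450 mg three times weekly. Reduction: 600/1,050 = 57%.
- Exposure: for the 16-patient study cited in Protocol 2.1, the median AUC and Cmax on 150 mg three times weekly, then on 150 mg daily, are given as "2307 ng/mL.h and 168 ng/mL, and 5010 ng/mL.h and 311 ng/mL". Cmax falls by (311 − 168)/311 = 46%, and AUC by (5,010 − 2,307)/5,010 = 54%.
- For individual dose adjustment in section 5.1.1, a low RBT Cmax "will be defined as < 250 ng/mL". The median of 168 lies below that.

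These figures show that the step is a substantial change of treatment. They do not measure tolerability.

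**4. How many participants**

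SAP 1.6 says accrual period 2 will not open, which leaves the planned 20 per arm of accrual period 1. The same 16-patient study reports "only one case of uveitis that occurred prior to starting LPV/r and one episode each of Grade 2 transaminitis and neutropenia reported", so no Grade 4 neutropenia is described. With 0 of 16, the one-sided 95% upper limit is 1 − 0.05^(1/16) = 17%. At an assumed 2-10%, the expected number per RBT arm is 20 × 0.02 = 0.4 to 20 × 0.10 = 2. The rate is an assumption.

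**The case against.** **The bottom level is coarse by design.** It means no permanent stop and no hold beyond the threshold; it does not claim that nothing was changed. The 7-day cut matches the interruption threshold that section 6.3.5 sets for recording TB-drug interruptions, and the companion variable for antiretrovirals (9.2.3.3.2) has the same structure. This stands: the ordering is correct as far as it goes, and the point is about completeness, not a wrong rule.

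**The reduction step may not occur.** In Arms A and C, RBT is given at 300 mg daily until antiretroviral therapy starts, "at which time the dose should be reduced to the 150 mg daily dose" (section 3.0). A site could therefore treat 150 mg daily as already reduced and go straight to the short hold in 7.2.4. The text does not settle this. On that reading the participant still lands in the bottom level if RBT restarts within 7 days, but a dose-reduction level would not pick the case up. This limits the remedy.

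**The event is counted elsewhere.** Grade 4 neutropenia enters 9.2.3.3.1 and the SAP 4.1 tables. This also stands. What goes unreported is the management step, since SAP 4.2 tabulates discontinuations only.

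**A new level would fill unevenly.** The protocol directs reductions for RBT and leaves rifampin to local practice, so a difference between arms in that level could reflect the rule and not worse tolerability. This is a reason to keep the three-level variable as it is and to make the fourth level supplementary.

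**Conclusion.** The gap is real and small. Endpoint 9.2.3.3.3 groups protocol-directed toxicity dose reductions of RBT with no management at all, so the only listed TB-drug management measure for objective 1.3.4 cannot show them. The consequence is an incomplete descriptive comparison on an endpoint that section 9.6.3 treats as exploratory, probably involving about 0-2 participants per RBT arm. That range rests on about 20 per arm and an assumed rate of 2-10%.

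A reader might infer that the omission raises the chance of wrongly declaring the RBT arms better tolerated. The documents do not support this. They give no rate of toxicity management in any arm, no rate of reductions in Arm B, and no specific test for this endpoint. Moreover, if reductions are ranked below long holds and stops, an RBT arm that has reductions where Arm B has holds and stops really has had milder management. No false-positive risk has been shown.

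Confidence is medium, chiefly because 7.2.4 can be read in two ways as to what counts as a reduced dose.

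**What to change.** Keep the three-level variable. Add a supplementary four-level version of 9.2.3.3.3, with dose reduction due to toxicity placed between the hold of more than 7 consecutive days and the bottom level. Apply it to any TB drug in any arm, including local reductions of rifampin. Exclude reductions made only for a high RBT Cmax, because Table 5.1 prescribes the same 150 mg three times weekly for that purpose, and flag cases with both a toxicity and a high Cmax. Report counts at each level by arm, beside 9.2.3.3.1. Endpoint 9.2.3.3.2, the SAP safety criteria and the primary analysis need no change.

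The cost is a line of endpoint wording, one more row of counts and a small attribution review. Section 6.3.5 already requires drug modifications to be recorded, and sections 6.3.5 and 6.3.9 require symptoms and laboratory toxicities that changed treatment to be recorded. The text does not say that a reason is kept for each dose change, so each reduction has to be linked to a toxicity by hand.

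Two downsides should be stated with the table. The new level will fill mainly from Arms A and C because of the protocol's RBT rule. Toxicity holds of 7 days or less without a dose reduction stay unranked, since section 6.3.5 names only TB-drug interruptions longer than 7 days for recording. This is a cheap improvement of low priority.

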### 9.3 Randomization and Stratification

The participants will be randomized 1:1:1 to three open-label arms using permuted blocks. Randomization will not be stratified.

## 9.4 Sample Size and Accrual

Accrual will take place in two periods. Accrual period 1 will enroll participants who will undergo an initial dose-finding period before continuing regular study follow-up through 72 weeks. Once review of the dose-finding period in accrual period 1 participants is complete, accrual period 2 will begin.

### 9.4.1 Sample Size and Accrual for Dose-Finding Study in Accrual Period 1 Participants

For the study design of the dose-finding study in participants enrolled during the accrual period 1, the primary driver is equivalence comparing day 12 ± 2 (after initiation of ART) RBT 24-hour AUC with control data derived from prior PK studies. Subject-level data for 500 studies were simulated with pre-specified sample sizes and no-effect boundaries (NEBs). For the simulation study data, geometric mean ratios (GMRs), mean GMR, and 90% confidence intervals were calculated. Based on this simulation study, eighteen evaluable participants per arm are needed for the dose-finding study in accrual period 1 participants to adequately evaluate PK parameters and safety. As shown in Table 9.1 below, a CV of 32% was assumed with three different NEBs. There is more than 90% power to have the 90% CI around the GMR fall entirely within the pre-specified NEB of 67%-150%.

Table 9.1. Probability (%) of Declaring Equivalence for the RBT PK Objective

Sample size		% diff	Prob declare equiv for NEB			Simulated data	
Alone	Co-drug	AUC	50%-200%	67%-150%	80%-125%	Mean GMR	Typical 90% CI
14	14	-30	87%	11%	1%	69.7%	(57.1%, 85.2%)
		-20	98%	44%	4%	79.9%	(65.4%, 97.6%)
		-10	100%	76%	12%	89.2%	(73.1%, 108.9%)
		-5	100%	89%	19%	95.4%	(78.2%, 116.3%)
		5	100%	90%	18%	104.2%	(85.4%, 127.1%)
		10	100%	83%	13%	109.2%	(89.4%, 133.4%)
		20	100%	57%	6%	120.4%	(98.7%, 146.8%)
18	18	30	96%	32%	1%	130.1%	(106.5%, 158.9%)
		-30	93%	9%	0%	69.9%	(58.7%, 83.2%)
		-20	100%	52%	5%	80.1%	(67.3%, 95.4%)
		-10	100%	90%	24%	90.3%	(75.9%, 107.5%)
		-5	100%	93%	30%	94.2%	(79.2%, 112.1%)
		5	100%	94%	30%	105.5%	(88.7%, 125.5%)
		10	100%	90%	26%	110.0%	(92.4%, 131.0%)
22	22	20	100%	70%	9%	119.0%	(99.9%, 141.7%)
		30	99%	36%	2%	130.6%	(109.6%, 155.7%)
		-30	98%	13%	0%	69.8%	(59.6%, 81.8%)
		-20	100%	55%	4%	79.5%	(68.0%, 93.0%)
		-10	100%	93%	31%	90.3%	(77.0%, 105.9%)

Sample size		% diff	Prob declare equiv for NEB			Simulated data	
Alone	Co-drug	AUC	50%-200%	67%-150%	80%-125%	Mean GMR	Typical 90% CI
		-5	100%	98%	45%	95.0%	(81.3%, 111.1%)
		5	100%	98%	46%	104.8%	(89.5%, 122.8%)
		10	100%	94%	31%	110.5%	(94.5%, 129.3%)
		20	100%	77%	10%	120.0%	(102.6%, 140.2%)
		30	100%	44%	3%	129.5%	(110.6%, 151.7%)

Participants who do not have day  $12 \pm 2$  (after initiation of ART) PK samples will not be replaced. Thus, we will enroll 20 participants in each arm, expecting 18 participants in each arm with evaluable PK data. (However, the accrual period 1 PK and safety interim analysis may lead to proposing additional accrual period 1 participants to assure an adequate PK assessment.)

Accrual will be suspended after the last participant is enrolled into the accrual period 1.

